The primary endpoints are the improved tolerance to the bronchoconstrictive effect (reduced airway hyperresponsiveness) of inhaled methacholine (methacholine PD₂₀) or a reduction in exhaled nitric oxide. The secondary endpoints are a reduction in markers of asthmatic lung inflammation; specifically serum cytokines, eosinophilia, and establishing pharmacokinetic parameters of biologically active components of ginger in adult asthmatics.

Design and Outcomes

A placebo controlled, double blind, randomized clinical pilot study of mild to severe asthmatics treated in a 1:1 ratio with oral ginger 1 gm twice per day or matching placebo. This will occur in the Columbia University Medical Center, The Johns Edsall-John Wood Asthma Center Outpatient Unit, [name].

Screening/Run-In Period Adults 18 and older, with physician diagnosed mild to severe persistent asthma will be screened. After reviewing and signing informed consent, subjects that fulfill inclusion and exclusion criteria will be invited to participate.

Day 0/Visit 1: Screening Visit: review of medical history, recording of medication use, physical exam by study MD or NP, scoring on ACT and basic spirometry before and after bronchodilator. Subjects will then be asked to continue their usual asthma medications for the 14-21 day run-in period.

Day 14-21/Visit 2: Subjects will be asked to withhold appropriate medications (long acting bronchodilator for 36 hours, short acting bronchodilator for 6 hours). Women of child bearing potential will have a urine pregnancy test checked. Checklist for methacholine will be reviewed with patient. If ACT remains ≤ 19 and FEV₁ > 60% predicted, subjects will undergo methacholine bronchoprovocation testing which involves inhaling increasing concentrations of nebulized methacholine until the measured FEV₁ decreases by 20% of the initial value measured after diluent inhalation, defined as the methacholine PD₂₀. If ACT is > 19, consistent with good asthma control, subjects will be terminated from the study.

Day 15-23 (1-2 days following V2)/Visit 3 Randomization Visit:

If ACT remains ≤ 19 , subjects will be randomized into 2 treatment groups; oral ginger (1g twice per day: Pure Encapsulations™) or matching placebo (*FDA IND in place*: # [REDACTED]). Ratio of randomization will be 1:1. An independent statistician will generate the randomization codes and allocations. The blinded study coordinator will retrieve the randomization allocation for each subject through RedCap. RedCap is an institutionally available automated system for randomization; the independent statistician will have direct oversight over the process. The blinded study team will not have access to the randomization codes.

At the randomization visit, women of child bearing potential will have a negative pregnancy test confirmed, subjects will be asked to complete an ACT to assess asthma control and a validated asthma quality of life questionnaire (Juniper mini AQLQ). Fractional excretion of nitric oxide (FeNO) will be measured using a Circassia Niox Vero machine with disposable filters. Pre-dose basic spirometry will be performed. 10ml of blood will be collected for measurement of baseline cytokines, biomarkers and blood eosinophil count. Subjects will be given their first dose of study drug and post-dose spirometry will be repeated one hour later.

A total of eight subjects will undergo pharmacokinetic (PK) measurements of the key metabolites of active ginger components. For those patients, an additional 35 ml of blood will be collected over an additional 7 times points (pre-dose, 0.5 hour, 1 hour, 2 hour, 3 hour, 4 hour, and 8 hour). The eight subjects will be selected through voluntary participation. The option will be provided to all subjects who sign the consent. Once there have been 4 subjects in Group A and 4 subjects in Group B selected, there will no longer be any additional subjects accepted to join the PK study.

Day 43-50/Visit 4: Subjects will be asked to withhold morning dose of the study drug the day of the study visit. Women of child bearing potential will have a negative pregnancy test confirmed. Subjects will be asked to complete an ACT to assess asthma control and a validated asthma quality of life questionnaire (Juniper mini AQLQ). FeNO will be measured using a Circassia Niox Vero machine with disposable filters. Basic spirometry will be performed, Methacholine test will be performed if subject meets safety criteria ($FEV_1 > 1.5L$ or 60% predicted). 10ml of blood will be collected for measurement of cytokines, biomarkers and blood eosinophil count. For those patients in PK group, an additional 35 ml of blood will be collected over an additional 7 times points (pre-dose, 0.5 hour, 1 hour, 2 hour, 3 hour, 4 hour, and 8 hour). Study drug will be administered in the clinic after the pre-dose PK blood draw.

Unused study medication will be collected and pill count will be recorded.

Day 71-78/Visit 5: Subjects will be asked to withhold morning dose of the study drug the day of the study visit. Women of child bearing potential will have a negative pregnancy test confirmed. Subjects will be asked to complete an ACT to assess asthma control and a validated asthma quality of life questionnaire (Juniper mini AQLQ). FeNO will be measured using a Circassia Niox Vero machine with disposable filters. Basic spirometry will be performed. Methacholine hyperresponsiveness will be measured if subject meets safety criteria ($FEV_1 > 1.5L$ or $>60\%$ predicted). 10ml of blood will be collected for measurement of cytokines, biomarkers and blood eosinophil count. For those patients in PK group, an additional 35 ml of blood will be collected over an additional 7 times points (pre-dose, 0.5 hour, 1 hour, 2 hour, 3 hour, 4 hour, and 8 hour). Unused study medication will be collected and pill count will be recorded. Study drug will be administered in the clinic after the pre-dose PK blood draw.

Sample Size and Population

Adults 18 and older, with physician diagnosed mild to severe persistent asthma will be screened. 36 participants will be randomized equally into two arms (18 per group); 1 gram of oral ginger extract twice a day for 28 days or matching placebo. Our sample size analysis requires 16 participant per group and with an anticipated 10% attrition rate, we will enroll 18/group.

Randomization will not be stratified in this pilot study.

The NIH National Asthma Education and Prevention Program (NAEPP) Guidelines for assessing asthma severity will be used by the PI to grade severity of asthma.¹

1. STUDY OBJECTIVES

1.1 Primary Objective

The primary endpoints are a clinically significant improvement in tolerance to inhaled methacholine (PD20) or a clinically significant decrease in exhaled nitric oxide. A clinically significant increase in tolerance to inhaled methacholine is defined as a 0.7 increase in the doubling dose for inhaled methacholine from the subjects baseline. A clinically significant decrease in exhaled nitric oxide is defined as a 20% decrease in subjects starting at a baseline of >50 ppb or a decrease of 10 ppb for subjects starting at a baseline of <50 ppb.

1.2 Secondary Objectives

- a. To determine if oral daily ginger extract intake;
 1. increases forced expiratory volume in one second (FEV1) by 100ml.
 2. decreases blood eosinophilia
 3. decreases asthma-associated cytokines in serum
- b. Establish pharmacokinetic parameters of biologically active components of ginger in adult asthmatics.

2. BACKGROUND AND RATIONALE

2.1 Background on Condition, Disease, or Other Primary Study Focus

The Centers for Disease Prevention and Control report that 9% of Americans have asthma which accounted for 1.8 million emergency room visits and 0.5 million hospitalizations in 2011 with a projected cost of \$56 billion.² Asthma is a chronic inflammatory disorder of the airways characterized by bronchoconstriction and airway inflammation marked by airway hyperresponsiveness. Current asthma therapies include short- and long-acting β -agonists to combat bronchoconstriction and inhaled corticosteroids (ICS) to reduce airway inflammation. These medications have important adverse effects, are not suitable for some patients, and have poor adherence.³ There are emerging targeted biologic therapies, especially directed against the Th2-high endotype of asthma, but these therapies are aimed at patients with severe asthma, are expensive, and do not address the multiple endotypes of asthma. Consequently, many Americans have increasingly turned towards complementary and alternative medicines for treating asthma.

Recent studies found that 60% of moderate asthmatics and 70% of severe asthmatics report using complementary and alternative (CAM) therapies to self-treat their asthma symptoms.⁴ Natural plant products in the forms of teas, topical ointments, and dietary supplements have been used for the relief of respiratory ailments including cough and bronchospasm.⁵ Of the many types of CAM therapies chosen by asthmatics, as many as 40% of asthmatics use herbal therapies to self-treat their asthma symptoms.⁴ The exact mechanism of action of these agents is unclear but may involve attenuation of the allergic cascade through blockade of IgE mediated inflammation, anti-inflammatory and antioxidant effects, and/or direct effects on acutely relaxing human airway smooth muscle (ASM).

2.2 Study Rationale

Recently we demonstrated that purified components of ginger (6-shogaol, 6-gingerol, 8-gingerol) acutely relaxed human airway smooth muscle (ASM) *in vitro*⁶ and our newest preliminary data shows that specific human metabolites of these components have potent ASM relaxing properties. Additionally, we have preliminary data showing that ginger components reduced lung inflammation in a mouse model of asthma. We demonstrated that the cellular mechanism by which ASM relaxation occurs is via inhibition of phospholipase C (PLC) a pivotal enzyme that mediates smooth muscle contraction as well as cytokine release from immune cells and airway structural cells.⁶ Thus, natural compounds that inhibit PLC can

target two key features of the pathophysiology of asthma; smooth muscle constriction and cytokine release. It is not possible to measure PLC activity directly in live human subjects, but it is possible to directly measure the functional effect of PLC inhibition; improved tolerance for inhaled methacholine and reduced inflammation which will be the key biological signatures measured in this 2 month clinical study of oral ginger in asthmatics. We contend that this proposal is highly responsive to the goals of this program as it (1) studies a natural product in a disease commonly encountered in primary care practice; (2) tests a natural botanical substance widely used as a dietary supplement for which sufficient early stage safety and mechanistic data justifies further clinical testing; (3) measures the bioavailability of the natural product and its major human metabolites; and (4) demonstrates primary biological signatures in patients.

Ginger is widely used as an over-the-counter oral dietary supplement. The formulation and amount of ginger used in this study (2g per day; Pure Encapsulations®) has been chemically characterized by HPLC and has been administered to patients at the oral amount (2 grams) for 28 days in multiple human studies measuring inflammatory mediators in colonic mucosal biopsies. We chose this formulation and dose based on its history of excellent tolerance in previous human studies. We chose to divide the 2g dose into 1g twice a day dosing to minimize the chance of gastrointestinal side effects while limiting the burden on subject dosing to twice a day to increase retention and compliance within the study. We have also demonstrated in pre-clinical studies in a mouse model of asthma that this dose reduces asthma-associated lung inflammation.

The incidence of side effects in a 28 day trials of 30 individuals were not significantly different in placebo versus ginger and no adverse events were greater than the NCI Common Toxicity Criteria Grade 1. In a second study of 27 individuals, no adverse event greater than NCI Common Toxicity Criteria Grade 1 was reported (no placebo comparison) and the leading complaints were gastrointestinal symptoms of eructation, heartburn or indigestion.⁷ In a third study of 20 patients consuming the same formulation in the same amount for the same duration (2g, Pure Formulations, 28 days) no statistically significant increase in adverse events occurred compared to placebo, no toxicities were greater than the NCI Common Toxicity Criteria Grade 1 and included bloating, nausea and heartburn.

There have been small numbers of studies reporting on possible inhibition of platelet aggregation by ginger. Ginger has been shown in an in vitro study to inhibit platelet aggregation with a potency similar to that of aspirin and in another study of human volunteers, to have a synergistic effect with nifedipine in platelet aggregation.⁸⁻¹⁰ A single case report has been published demonstrating epistaxis in a woman who was being treated with Coumadin who subsequently started taking ginger.¹¹ Subjects taking anti-coagulation will be excluded from participation, though subjects taking aspirin alone will be included in the study since there have been no studies or reports of increased bleeding risk with aspirin and ginger combined.

3. STUDY DESIGN

A placebo controlled, double blind, randomized clinical pilot study of mild to severe asthmatics treated in a 1:1 ratio with oral ginger 1 gm twice per day or matching placebo.

18 subjects will be assigned to each of two arms (ginger vs. placebo). This is defined by a power analysis requiring 16 subjects per arm and a 10% projected attrition rate. Subjects will be evaluated 5 times during the study, at screening, baseline methacholine testing, at the initial randomization visit and at days 28 and 56 while taking ginger or placebo.

The primary outcomes will be the improved tolerance to the bronchoconstrictive effect (reduced airway hyperresponsiveness) of inhaled methacholine (methacholine PD₂₀) or a reduction in exhaled nitric oxide. Secondary outcomes will include an improvement in baseline FEV1 of 100ml, a reduction in eosinophilia or a reduction in asthma associated serum cytokines. An additional secondary outcome will be defining the pharmacokinetic profile of active components of ginger in adult asthmatics.

Grant phase	Spec. Aim	Primary outcome	Clinically Significant Change [ref]	Means ± S.D; examples from literature [ref] (units)	Sample Size \group	# of groups	Sample size required	Sample Size required with 10% attrition
R61	1	Mch PD ₂₀ doubling dose	Increase of 0.7 in Mch doubling dose ¹²	1.07 ± 0.6 1.73 ± 0.6 (Mch doubling dose) ¹²	14	2 2g/day ginger placebo	28	32
	2	Exhaled nitric oxide	20% decr for >50 ppb or decr of 10ppb for <50ppb ¹³	74 ± 37 37 ± 34 (ppb) ¹⁴	16	2 2g/day ginger placebo	32	36 for aims 1&2

Outpatient; The John Edsall-John Wood Asthma Center at the Columbia University Medical Center

Individual enrollment: 78 +/- 7 days. Enrollment period 12 months, Entire trial (first subject screened to last patient completed): 20 months.

Screening/Run-In Period

Adults 18 and older, with physician diagnosed mild to severe persistent asthma will be screened. After reviewing and signing informed consent, subjects that fulfill inclusion and exclusion criteria will be invited to participate.

Day 0/Visit 1: Screening Visit: review of medical history, recording of medication use, physical exam by study MD or NP, scoring on ACT and basic spirometry before and after bronchodilator. Subjects will then be asked to continue their usual asthma medications for the 14-21 day run-in period.

Day 14-21/Visit 2: Subjects will be asked to withhold appropriate short and long acting bronchodilators for the appropriate period. Women of child bearing potential will have a urine pregnancy test checked. Checklist for methacholine will be reviewed with patient. If ACT remains ≤ 19 and FEV1 > 60% predicted, subjects will undergo methacholine bronchoprovocation testing which involves inhaling increasing concentrations of nebulized methacholine until the measured FEV1 decreases by 20% of the initial value measured after diluent inhalation, defined as the methacholine PD20. If ACT is > 19, consistent with good asthma control, subjects will be terminated from the study.

Day 15-23 (1-2 days following V2)/Visit 3 Randomization Visit:

If ACT remains ≤ 19, subjects will be randomized into one of two treatment groups; oral ginger (1g twice per day: Pure Encapsulations™) or matching placebo (*FDA IND in place: # [REDACTED]*). Ratio of randomization will be 1:1.

At the randomization visit women of child bearing potential will have a negative pregnancy test confirmed, subjects will be asked to complete an ACT to assess asthma control and a validated asthma quality of life questionnaire (Juniper mini AQLQ). Fractional excretion of nitric oxide (FeNO) will be measured using a Circassia Niox Vero machine with disposable filters. Pre-dose basic spirometry will be performed. 10ml of blood will be collected for measurement of baseline cytokines, biomarkers and blood eosinophil count. Subjects will be given their first dose of study drug and post-dose spirometry will be repeated one hour later.

A subset of subjects (4 males and 4 females) will undergo pharmacokinetic (PK) measurements of the key metabolites of active ginger components. For those patients, an additional 35 ml of blood will be collected over an additional 7 times points (pre-dose, 0.5 hour, 1 hour, 2 hour, 3 hour, 4 hour, and 8 hour).

Day 43-50/Visit 4: Subjects will be asked to withhold morning dose of the study drug the day of the study visit. Women of child bearing potential will have a negative urine pregnancy test confirmed. Subjects will be asked to complete an ACT to assess asthma control and a validated asthma quality of life questionnaire (Juniper mini AQLQ). FeNO will be measured using a Circassia Niox Vero machine with disposable filters. Basic spirometry will be performed, Methacholine test will be performed if subject meets safety criteria ($FEV_1 > 1.5L$ or 60% predicted). 10ml of blood will be collected for measurement of cytokines, biomarkers and blood eosinophil count. For those patients in PK group, an additional 35 ml of blood will be collected over an additional 7 times points (pre-dose, 0.5 hour, 1 hour, 2 hour, 3 hour, 4 hour, and 8 hour). Study drug will be administered in the clinic after the pre-dose PK blood draw.

Unused study medication will be collected and pill count will be recorded.

Day 71-78/Visit 5: Subjects will be asked to withhold morning dose of the study drug the day of the study visit. Women of child bearing potential will have a negative pregnancy test confirmed. Subjects will be asked to complete an ACT to assess asthma control and a validated asthma quality of life questionnaire (Juniper mini AQLQ). FeNO will be measured using a Circassia Niox Vero machine with disposable filters. Basic spirometry will be performed. Methacholine hyperresponsiveness will be measured if subject meets safety criteria ($FEV_1 > 1.5L$ or $>60\%$ predicted). 10ml of blood will be collected for measurement of cytokines, biomarkers and blood eosinophil count. For those patients in PK group, an additional 35 ml of blood will be collected over an additional 7 times points (pre-dose, 0.5 hour, 1 hour, 2 hour, 3 hour, 4 hour, and 8 hour). Unused study medication will be collected and pill count will be recorded. Study drug will be administered in the clinic after the pre-dose PK blood draw.

Randomization is a process that assigns participants/subjects by chance (rather than by choice) into specific groups, typically for clinical research and clinical trials. An independent statistician will generate the randomization codes and allocations. The blinded study coordinator will retrieve the randomization allocation through RedCap at the time of the randomization visit. RedCap is an institutionally available automated system for randomization; the independent statistician will have direct oversight over the process. The blinded study team will not have access to the randomization codes. In this module, randomization model is defined as Drug A and Drug B in a 1:1 ratio. Drug A and Drug B may refer to placebo or active drug, however they are left coded as such to ensure blinding. The module creates a template allocation table, which the user uses to structure the randomization table to be imported. The module also monitors the overall allocation progress and assignment of randomized subjects to ensure equal proportions of active drug and placebo. Only one site member will be allowed randomization privileges, but the site will confirm, and lock the specific data field to ensure that no data is altered after randomization. There is no stratification, and there are no variable block sizes.

All evaluations and blood draws will be completed at a single site at a single center, the outpatient clinic of The John Edsall-John Wood Asthma Center at the Columbia University Medical Center. Blood eosinophils will be measured by the Center for Advanced Laboratory Medicine (CALM) with the Department of Pathology and Cell Biology at Columbia University Medical Center. Plasma cytokines will be measured by multiplex array in the laboratory of [name], at Columbia University and the metabolite measurements within the PK studies will be performed by [name], [name].

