5.2 Handling of Study Interventions

The study drug (~500mg capsules) (ginger extract from Pure Encapsulations) and matching placebo have been provided to our research pharmacy and packaged (120 capsules/bottle) by the manufacturer. Each bottle is labeled 'A' or 'B' and the code is held by the research pharmacy. Study drug is stored at room temperature; temperature logs are maintained by Research Pharmacy. For distribution to study subjects, the clinical research coordinator will obtain the appropriately labeled bottle from the research pharmacy on the day of the study visit and distribute to the subject. Unused study drugs and placebo will be destroyed.

Study intervention accountability records will be the case report source documents that will be stored within the study binder and include (1) inclusion/exclusion documentation; (2) medical history; (3) concomitant medications; (4) adverse events; (5) methacholine challenge data; (6) individual source documents for visits 1-5.

There are no lifestyle/behavioral interventions in this study. Not applicable.

The placebo is in an identically appearing capsule as the study compound. Taste of placebo and ginger is matched as per manufacturer.

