6.2.1 Screening Evaluation

Adults 18 and older, with physician diagnosed mild to severe persistent asthma will be screened. After reviewing and signing informed consent, subjects that fulfill inclusion and exclusion criteria will be invited to participate.

Consenting Procedure

Single informed consent describing screening and study procedures.

The study PI ([name]) or the research study coordinator ([name]) will conduct the consent process.

[name] is a professor of medicine and pulmonologist and director of the John Edsall-John Wood Asthma Center at Columbia University Medical Center. [name], B.S. has over 3 years of experience as a clinical research coordinator and has experience consenting and studying pulmonary

patients during clinical studies in the John Edsall-John Wood Asthma Center.

Any changes in the consent form will only occur after approval from the institutional IRB and the NCCIH.

Documentation of the consent process and consent forms will be retained in a research study binder.

Screening

Visit 1: Screening Visit

Sequence of events:

- Identify patients that are adults 18 and older with physician-diagnosed mild to severe persistent asthma
- Sign informed consent
- Fulfill inclusion and exclusion criteria
- Review of medical history
- Record Demographics
- Recording of medication use
- Physical exam including vital signs by study MD or NP
- Urine pregnancy test for women of child bearing age
- Scoring on ACT ≤ 19
- Scoring on basic spirometry before and after bronchodilator

Required to be eligible:

- Patients that are adults 18 and older with physician-diagnosed mild to severe persistent asthma
- Signing informed consent
- Fulfill inclusion and exclusion criteria
- Using inhaled corticosteroids with or without inhaled long acting beta agonists or anti-muscarinics.
- Scoring on ACT ≤ 19
- Negative urine pregnancy test for women of child bearing age

Screening must be completed 14-21 days prior to visit 2 during which the ACT score will be confirmed to be ≤ 19 , and the baseline FEV1 is $\geq 60\%$ of predicted (or 1.5L); Baseline methacholine PD20 will be determined at V2 as a subsequent eligibility criterion.

Visit 2; Day 14 to 21:

- Administer ACT. If ACT remains ≤ 19 , proceed . If ACT > 19 consistent with good asthma control, terminate from study.
- Confirm medication washouts (reschedule if not met).
- Spirometry

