9.2 Sample Size and Randomization

We utilized published literature to identify the magnitude of change in our primary outcomes that are clinically relevant. As illustrated in the table in section 3, we calculated a need of 14 subjects per arm for the methacholine measurement and 16 subjects per arm for the exhaled nitric oxide assessment (same subjects studied in methacholine and exhaled nitric oxide assays). Thus we need 16 subjects per arm and anticipate a 10% attrition rate overall requiring 36 subjects. As illustrated in the table in section 3, an enhanced tolerance to inhaled methacholine of 0.7X the doubling dose is considered clinically significant.¹² We anticipate a S.D. of 0.6 in both groups and aim to achieve 80% power at the 0.05 significance level. This requires 14 subjects for each of the two arms. For exhaled nitric oxide with baselines starting at >50ppb, a 20% decrease is considered clinically significant. We expect a S.D. of ~ 37 and aim to achieve 80% power at the 0.05 level and will thus require 16 subjects for each of two arms.

Treatment Assignment Procedures

Subjects will be randomized to treatment A or B in a blinded fashion using the randomization algorithm within REDCap. The randomization module in REDCap implements a defined randomization model within the project, allowing the site to randomize the subjects. In this module, randomization model is defined as Drug A and Drug B in a 1:1 ratio. Drug A and Drug B may refer to placebo or active drug, however they are left coded as such to ensure blinding. The module creates a template allocation table, which the user uses to structure the randomization table to be imported. The module also monitors the overall allocation progress and assignment of randomized subjects to ensure balanced proportions of active drug and placebo. Only one site member will be allowed randomization privileges, but the site will confirm, and lock the specific data field to ensure that no data is altered after randomization. There is no stratification, and there are no variable block sizes.

Trial randomization codes for each individual subject will be retained within the REDCap data set as treatment A or B. The independent statistician retains the identity of A or B and does not disclose this to the study conductors. The planned breaking of the code will occur after data analysis is complete. Unplanned breaking of the code will occur if a medical condition mandates such an action.

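### Variable block sizes are ruled out while the coordinator handles bottles marked with one of two trial-wide letters: fixed blocks would make some letters certain in advance, and no blocks would leave balance to chance

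*Combined protocol and SAP*

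**What the plan says.** Section 3 states: "There is no stratification, and there are no variable block sizes". The same sentence stands in Sections 4.3, 6.2.2 and 9.2. No section says whether blocks are used at all, or of what size. The only statement on balance is that the REDCap module monitors assignments so that the arms stay equal. That is an aim, and no mechanism is given. The Précis plans 36 participants, 18 per arm.

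On who sees what:

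- **Consent (6.2.1):** the PI or the research study coordinator "will conduct the consent process".
- **Allocation (3):** "The blinded study coordinator will retrieve the randomization allocation through RedCap at the time of the randomization visit". Only one site member holds randomisation privileges.
- **Labels (5.2):** "Each bottle is labeled 'A' or 'B' and the code is held by the research pharmacy".
- **Dispensing (5.2):** "the clinical research coordinator will obtain the appropriately labeled bottle from the research pharmacy on the day of the study visit".
- **Data set (9.2):** "Trial randomization codes for each individual subject will be retained within the REDCap data set as treatment A or B".
- **PK subset (Précis):** intake closes "Once there have been 4 subjects in Group A and 4 subjects in Group B selected", which requires someone to count letters. Sections 3 and 6.2 instead describe the subset as four men and four women.

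On the protective side, an independent statistician generates the list, the study team has no access to the codes, and the letters do not name the drug.

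**The concern.** Fixed blocks are often tolerable in a double-blind trial because site staff see a different kit number for each participant and so cannot follow the sequence. Here the labels are two letters, each tied to one arm for the whole trial. One person at a single site can therefore see the full run of assignments as it builds up. With a fixed block size, known or inferred, part of the remaining sequence then follows with certainty.

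What is at stake is allocation concealment. If the meaning of a letter became known, someone who takes consent could foresee some of the next treatments. Excluding variable block sizes is a stated choice, and the alternative costs very little. If the sentence instead means that no blocks are used, the promised 18 per arm rests on chance.

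**Working it through.** **The plan's own figure.** For FeNO the Section 3 table gives means of 74 and 37 ppb, a difference of 37, and Section 9.2 gives an SD of about 37. At two-sided 0.05 (sidedness assumed) and 80% power, n per arm = 2 × (1.96 + 0.84)² × 37²/37² = 15.7, so 16. With 10% attrition, 16/0.9 = 17.8, so 18 per arm and 36 in total. The plan's figure reproduces.

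**Branch 1: one fixed block size.** The size is not in the documents, so a range is shown. Write the block as b = 2h.

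- A letter is certain once the other letter has been used h times in that block. The expected number of certain letters per block is 2h/(h + 1), a share of 1/(h + 1).
- The best guess names whichever letter is behind and tosses a coin when they are level. Expected correct guesses per block are h + ½ × [4^h / C(2h, h) − 1]. For b = 4 this is 2 + ½ × (16/6 − 1) = 2.83 of 4.

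| Block size | Certain letters of 36 | Share certain | Best-guess accuracy |
|---|---|---|---|
| 2 | 18 | 50% | 75% |
| 4 | 12 | 33% | 71% |
| 6 | 9 | 25% | 68% |
| 12 | 5.1 | 14% | 64% |
| 36 (one list of 18 A and 18 B) | 1.9 | 5% | 59% |

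Chance accuracy is 50%.

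**Branch 2: no blocks.** The number in one arm is Binomial(36, 0.5).

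- P(exactly 18/18) = C(36, 18)/2³⁶ = 9,075,135,300/68,719,476,736 = 13.2%.
- P(smaller arm 15 or fewer) = 40.5%; 14 or fewer, 24.3%; 12 or fewer, 6.5%.
- Two-sample t-test power at a standardised effect of 37/37 = 1.0, before attrition: 83.0% at 18/18, 81.1% at 14/22 and 78.5% at 12/24. Averaged over all splits it is 81.9%, a loss of 83.0 − 81.9 = 1.1 points.

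**After the change.** Lists of 36 were simulated from randomly ordered blocks, each size equally likely, with an observer who knows the set of sizes but not their order.

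- Sizes 2, 4 and 6: about 4% of letters certain, best-guess accuracy about 70%.
- Sizes 4, 6 and 8: best-guess accuracy about 68%.

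Mixing sizes removes most of the certainty. It barely changes guessing, because the arms return to balance at the end of every block, so the lagging letter is always the better guess.

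**The case against.** The strongest reply is that what can be predicted is a letter, not a treatment. Section 9.2 has the independent statistician keep the meaning of A and B, and Section 5.2 says appearance and taste are matched. The cited ginger-versus-placebo studies found no significant difference in side effects, so symptoms are a weak clue. PK plasma is shipped to another laboratory, and nothing says results return during enrolment. Entry depends largely on ACT, FEV1 and methacholine criteria, and Visit 3 follows Visit 2 by one or two days, so there is limited room to act on a prediction. A single list of 18 A and 18 B also fits the text. It would balance exactly at 36 and leave only 5% of letters certain.

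Most of this stands, and it rules out several stronger readings:

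- A reader might infer that the coordinator can foresee who gets ginger. The documents do not support that while the letters stay masked.
- A reader might infer that small fixed blocks are in use, or that the coordinator controls all screening and scheduling. Neither is stated, and consent may be taken by the PI instead.
- A reader might take the 40.5% chance of an arm below 16 to mean a badly underpowered trial. The average loss is about 1 point. This is also the less likely branch, since the plan promises equal arms.

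What the reply does not remove is the effect of having only two letters. Section 6.2.3 lets the PIs break the blind over one participant's safety, and that single act would decode both letters for everyone. Custody of the code is also stated inconsistently: Section 5.2 and part of Section 9.2 place it with the research pharmacy, while Section 6.2.3 and another part of Section 9.2 place it with the independent statistician. Nothing says that block size is withheld from the site.

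**Conclusion.** The concern holds as a conditional weakness in allocation concealment that is cheap to correct. It does not show that the trial is biased. Under fixed blocks of 6 down to 2, 25% to 50% of letters are certain in advance, falling to 5% for one list of 36. These figures assume a block size, which the plan does not give, and an observer who sees the earlier letters and knows or infers that size. Selection also requires that a letter has been decoded and that there is room to act on it.

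Without blocks, exact balance occurs in 13% of trials at little cost in power, so predictability is the weightier branch. A reader might expect mixed blocks to make the sequence unguessable. They do not: certain letters nearly vanish, but best-guess accuracy stays at 68% to 70%. The shared label is a separate weakness that block sizes do not address.

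**What to change.** Before the first randomisation:

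1. Have the independent statistician generate the REDCap table with randomly permuted blocks of mixed sizes not disclosed to the site. A 2/4/6 mix would serve; 4/6/8 lowers best-guess accuracy slightly further.
2. Replace the sentence in Sections 3, 4.3, 6.2.2 and 9.2 with a statement that permuted blocks of varying size are used and that the sizes are held by the independent statistician. Stratification is not needed.
3. Preferably, show the coordinator a participant-specific bottle number in place of A or B, so that one unblinding does not decode the rest.

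If randomisation has already begun, record the method and block size actually used and who knew them.

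The cost is one new table, relabelling of bottles if step 3 is taken, and a possible final imbalance of a few patients. The difference between arms cannot exceed half the largest block, that is 3 for blocks up to 6 and 4 for blocks up to 8.
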